17.2.2. ANALYSIS OF OTHER EFFICACY VARIABLES

17.2.2.1. Analysis of All Other Efficacy Variables

Actual and prescribed PN/IV and EN data will be analyzed and summarized separately. However, visit-level listings for average daily weight-normalized PN/IV volume, caloric intake, days per week and hours per day of PN/IV support, will present actual and prescribed data side-by-side.

For the variables of pre-specified % reduction in PN/IV volume, the number and percentage of subjects will be presented by visit and treatment arm and dose group. Baseline values, post-baseline values, change from baseline and percent change from the baseline in PN/IV support will be summarized by visit and treatment arm and dose group using descriptive statistics including number of subjects, mean, standard deviation, median, minimum and maximum.

Document:	\\quintiles.net\Enterprise\Apps\sasdata\SASa\sas\Shire\Teduglutide\Biostatistics\Documentation\SAP\TE D-C14-006_SAP_Final_V1.0_20170714		
Author:	PPD	Version Number:	Final V1.0
		Version Date:	14Jul2017
Template No:	CS_TP_BS016 – Revision 3	Reference:	CS_WI_BS005
Effective Date:	01May2012		

18. STUDY DRUG EXPOSURE

The extent of exposure is defined as the number of days on treatment. The number and percentages of subject will be tabulated for extent of exposure categorized into weeks (<4, 4-<12, 12-<24, >=24). Exposure summaries will be presented by teduglutide dose group (excluding the standard of care treatment arm) for the ITT, PP and SAF Analysis Sets. The study drug administration and study drug accountability data which are collected on the CRF will be listed.

Compliance and dose interruptions are not taken into account for the extent of exposure.

Information about interruptions of study drug by investigator decision (start date of interruption, date study drug resumed, and reason for interruption) will be included in data listings.

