6.1.1.2 Procedures for Reporting Adverse Events

Adverse events may be spontaneously reported by the subject or subject's parent/guardian, obtained through nonleading questioning, or noted during examination of a subject. All AEs and SAEs will be recorded from the signing of the informed consent form (ICF) and, if applicable, the informed assent form, through the last study visit (Visit 28 or EOS). SAEs will be monitored with a telephone call by the investigator, as necessary, for approximately 4 weeks after the last dose of study drug or until resolution or until the SAE is judged by the investigator to have stabilized.

As they occur, new AEs will be recorded sequentially on the AE page of the eCRF. The AE term should note the diagnosis whenever possible, not the individual signs or symptoms (eg, myocardial infarction should be recorded rather than chest pain, elevated cardiac enzymes, and abnormal ECG). Also recorded are:

- Start and stop date and time
- Whether the event is continuing
- Frequency (intermittent, continuous)
- Intensity (mild, moderate, severe)
 - Mild: usually transient, requiring no special treatment and generally not interfering with usual daily activities
 - Moderate: usually ameliorated by simple therapeutic maneuvers and impairs usual activities

- Severe: requires vigorous therapeutic intervention and interrupts usual activities; hospitalization may or may not be required.
- Relationship to study drug (not related, related): identify relationship as “related” if a causal relationship between the investigational product and an AE is at least a reasonable possibility (ie, the relationship cannot be ruled out)
- Whether the AE is serious (ie, an SAE). If identified as an SAE, the AE should be reported on the SAE form according to Section 6.1.2 below
- Actions taken (none; study drug dose changed, interrupted, or discontinued; other medication change; nondrug therapy)
- Outcome (resolved, resolved with sequelae, ongoing, fatal). An individual AE receives only one outcome.

Adverse events that are related to study drug and not resolved at the end of treatment will be followed by the site until resolution or until the AE is judged by the investigator to have stabilized.

Laboratory values, blood pressure, ECG evaluations, and clinical findings at the scheduled physical examinations must be reported as AEs if they:

- Are considered clinically significant by the investigator
- Fulfill SAE criteria, and/or

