6.1.4 Dose Interruption of Individual Subjects

Teduglutide administration for an individual subject may need to be stopped if the subject has an adverse event of special interest (see risks in table below) that is severe in intensity [Grade 3 or higher as defined by the National Cancer Institute’s Common Terminology Criteria for Adverse Events (CTCAE)]. This may occur if an event is attributable to study drug or a subject experiences an unexplained CTCAE Grade 3 or higher that is not reasonably related to the underlying disease process. The determination of length of the discontinuation, temporary or permanent, depends on the clinical situation.

Investigators and the DSMB should be guided by the descriptions of Grade 3 and 4 events below, as they relate to identified risks associated with the administration of teduglutide.

Identified Risk	Grade 3 Description	Grade 4 Description
Gastrointestinal Disorders		
Colorectal polyps	Severe or medically significant but not immediately life threatening; hospitalization or prolongation of existing hospitalization indicated; disabling; limiting self-care activities of daily living	Life-threatening consequences; urgent intervention indicated
Intestinal Obstruction	Hospitalization indicated; elective operative intervention indicated; limiting self-care activities of daily living; disabling	Life-threatening consequences; urgent operative intervention indicated
Gallbladder and Bile Duct Disease		
Cholecystitis	Severe symptoms; radiologic, endoscopic or elective operative intervention indicated	Life-threatening consequences; urgent operative intervention indicated
Gallbladder perforation	Not Applicable	Life-threatening consequences; urgent intervention indicated
Gallbladder obstruction	Symptomatic and severely altered gastrointestinal function; tube feeding, total parenteral nutrition or hospitalization indicated; nonemergent operative intervention indicated	Life-threatening consequences; urgent operative intervention indicated

Identified Risk	Grade 3 Description	Grade 4 Description
Gallbladder infection	Intravenous antibiotic, antifungal, or antiviral intervention indicated; radiologic, endoscopic, or operative intervention indicated	Life-threatening consequences; urgent intervention indicated
Alkaline Phosphatase increased	> 5.0 to 20.0 x Upper limit of normal	> 20.0 x Upper limit of normal
Blood bilirubin increased	> 3.0 to 10.0 x Upper limit of normal	> 10.0 x Upper limit of normal

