8.4 Other Variables

Other variables will be analyzed by treatment group including:

- Subject disposition
- Duration of study drug exposure
- Subjects will be considered compliant if study drug was taken according to protocol and assigned treatment group for $\geq 80\%$ of doses. Data will be taken from the Study Drug Accountability completed by the site staff. The number and percentage of subjects who were compliant will be presented by treatment group.
- The number and percentage of subjects who complete the study, are lost to follow up, or discontinued from the study (including reason for study withdrawal) will be summarized by treatment group.
- The study drug dose by duration will be summarized by treatment group.

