4. STUDY DESIGN

4.1. GENERAL DESCRIPTION

This study will include 2 treatment arms: a teduglutide treatment arm and a standard of care treatment arm. Subjects in both arms will participate in a 2-week minimum screening period, a 24-week treatment period, and a 4-week follow-up period. During the screening period, subjects will choose into which arm to enroll. During the 24-week treatment period, subjects in the standard of care treatment arm will receive standard medical therapy of SBS, while those in the teduglutide treatment arm will receive daily subcutaneous injections of teduglutide (study drug) in addition to standard medical therapy. The teduglutide treatment arm subjects will be randomized 1:1 in a double-blinded manner into two parallel teduglutide dose groups: 0.025 mg/kg/day and 0.05 mg/kg/day. Randomization across dose groups will be stratified by age: <1 year, 1 to <12 years, 12 to <17 years, and 17 to <18 years.

All subjects will be screened for a minimum of 2 weeks prior to start of treatment to verify the requirements for nutritional support for each subject and to ensure adherence to eligibility parameters. After screening, the 24-week treatment period will consist of site visits at baseline, weekly for the first 2 weeks (week 1 and 2), and then every other week through week 12 (week 4, 6, 8, 10, and 12). For the remainder of the treatment period, visits at the sites will be conducted every 3 weeks (at week 15, 18, 21, and 24). Telephone contacts will be made on all other weeks during the treatment period. The subjects in both arms will follow the same visit schedule. At all site visits and telephone contacts, safety will be monitored and nutritional

Document:	\\quintiles.net\Enterprise\Apps\sasdata\SASa\sas\Shire\Teduglutide\Biostatistics\Documentation\SAP\TE D-C14-006_SAP_Final_V1.0_20170714		
Author:	PPD	Version Number:	Final V1.0
		Version Date:	14Jul2017
Template No:	CS_TP_BS016 – Revision 3	Reference:	CS_WI_BS005
Effective Date:	01May2012		

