18.1. DERIVATIONS

The extent of exposure in days will be calculated as:

$$\text{Extent of exposure (days)} = (\text{date of last study drug administration} - \text{date of first study drug administration}) + 1.$$

The date of first study drug administration is collected on the eCRF “First SC Injection” form. The date of last study drug is collected on the eCRF “End of Treatment” form.

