19.1.3. AEs LEADING TO DISCONTINUATION OF STUDY DRUG

AEs leading to permanent discontinuation of study drug will be identified by the “Study drug discontinued” response for action taken with study treatment in the Adverse Events Form of the eCRF.

Separate listings will be provided for AEs leading to permanent discontinuation of study drug.

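### Exposure is calendar time and AE-driven drug action is summarized only for discontinuation, so a resumed hold of up to 33 of 168 days changes neither the exposure category nor the compliant count

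*SAP*

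**What the plan says.** **Exposure.** SAP 18.1 computes extent of exposure as the "date of last study drug administration" minus the first administration date, plus 1. SAP 18 adds: "Compliance and dose interruptions are not taken into account for the extent of exposure". The one exposure table it names reports "extent of exposure categorized into weeks (<4, 4-<12, 12-<24, >=24" weeks, by dose group. Interruptions decided by the investigator go to listings, with start date, resumption date and reason.

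**AE-driven drug action.** SAP 19.1.3 says that "AEs leading to permanent discontinuation of study drug will be identified by the" discontinued response in the action-taken field. The overall summary of treatment-emergent AEs (TEAEs) in SAP 19.1 has categories for discontinuation and death. It has none for interruption or dose change.

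**Holds are foreseen and recorded.** Protocol 6.1.4 allows dosing to be stopped for severe events of special interest: "The determination of length of the discontinuation, temporary or permanent, depends on the clinical situation". Protocol 5.3.2 names adverse events and hospitalization among the possible reasons for interruption. Protocol 6.1.1.2 has the AE page record "Actions taken (none; study drug dose changed, interrupted, or discontinued; other medication change; nondrug therapy".

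**Compliance.** SAP 15.1 divides the diary days marked Yes by the days from first to last dose and keeps interruption days in the denominator. SAP 15 summarizes the percentage and the number of subjects above 80% by treatment group. SAP 6.4 makes non-compliance a possible reason for exclusion from the per-protocol set.

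**The concern.** The objective includes safety and tolerability, and two doses are randomized against each other. If one dose leads to more temporary holds for adverse events, that is direct evidence on tolerability. As planned, a dose group with several such holds and one with none could show the same exposure table and the same AE counts by drug action.

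SAP 18 also describes the calendar extent as days on treatment. For a child whose dosing was held and resumed, that label includes days without drug. Protocol 4.1 plans at least 10 children per arm, so each such child is worth up to 10 percentage points in a category table.

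**Working it through.** The documents give no figure of their own to reproduce, so the SAP formulas are applied to a model course.

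**Inputs**
- Treatment length T: SAP 4.1 plans "a 24-week treatment period, and a 4-week follow-up period", so T = 24 × 7 = 168 days.
- Hold length k: assumed, because the documents give no figure.
- Assumptions: dosing resumes and continues to day 168, and every day outside the hold is marked Yes.

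**Formulas**
- SAP extent = last dose date − first dose date + 1 = 168, whatever k is.
- Days on drug = 168 − k.
- Compliance = (168 − k) / 168 × 100.

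| Days held (k) | SAP extent and category | Days on drug (weeks) | Compliance | Above 80%? |
|---|---|---|---|---|
| 0 | 168, >=24 weeks | 168 (24.0) | 100% | Yes |
| 14 | 168, >=24 weeks | 154 (22.0) | 91.7% | Yes |
| 28 | 168, >=24 weeks | 140 (20.0) | 83.3% | Yes |
| 33 | 168, >=24 weeks | 135 (19.3) | 80.4% | Yes |
| 34 | 168, >=24 weeks | 134 (19.1) | 79.8% | No |
| 56 | 168, >=24 weeks | 112 (16.0) | 66.7% | No |
| 84 | 168, >=24 weeks | 84 (12.0) | 50.0% | No |

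**Threshold.** (168 − k) / 168 > 0.80 requires k < 33.6, so 33 days (4.7 weeks) is the longest hold that still counts as compliant. Up to that length the child stays in the top exposure category, counts as compliant, and is not excluded from the per-protocol set for non-compliance.

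**Group level.** Take 10 children, nine at 100% and one with a 28-day hold. Mean compliance is (9 × 100 + 83.3) / 10 = 98.3%. A reader of the group mean would hardly notice the hold.

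**If dosing does not resume.** Extent ends at the true last dose. A last dose on day 84 gives 84 / 7 = 12.0 weeks, with no overstatement.

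**Would the existing week categories be enough for days on drug?** A 1-day hold gives 167 days (23.9 weeks) and an 84-day hold gives 84 days (12.0 weeks). Both fall in 12-<24 weeks, so the categories alone would not tell a trivial hold from a long one.

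**The case against.** The strongest reply is that calendar extent plus compliance is a disclosed two-part convention. For each child their product recovers the days dosed (168 × 83.3% = 140). Investigator-ordered holds are listed with dates and reason, and with about 20 treated children and a purely descriptive plan a listing can be read in full. Protocol 8.2 does not call for a summary of AEs leading to interruption, so the SAP delivers what that section asks for. The shells are in a separate file (SAP Appendix 4), and SAP 19.1 defers detail of the overall AE summary to the templates, so such a row may already exist there.

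Much of this stands. It makes this a reporting gap and not a hidden result. It does not close the gap: the product is not a planned output, it mixes holds with missed doses, and the listing does not give the reader a count by dose group.

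Two stronger readings are tempting, and the documents do not support them.
- *A reader might infer that a child held for weeks would look fully exposed and trouble-free throughout the report.* That is not so. Compliance falls, a hold of 34 days or more drops the child out of the compliant count, the hold is listed, and the event itself stays in the TEAE tables by term, severity, seriousness and relationship.
- *A reader might infer that SAP 18 breaks protocol 8.4*, which says: "The study drug dose by duration will be summarized by treatment group". This cannot be tested. The SAP is based on Amendment 4, while the change history of the supplied protocol ends at Amendment 2. A table of duration categories by dose group could also be read as meeting that sentence.

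**Conclusion.** The gap is real but limited. No named table separates time on drug from calendar time, and none counts children whose dosing was interrupted or changed because of an AE. On the stated assumptions (a 168-day course, dosing resumed, every other day marked Yes), a hold of up to 33 days alters neither the exposure category nor the count above 80% compliance. A 28-day hold is reported as 168 days when 140 were on drug.

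The practical effect depends on the number and length of holds, which are unknown and may be zero. It also depends on the unseen shells. The change is worth making because the data are already collected and bear directly on the tolerability of the two doses.

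**What to change.** In SAP 18:
- Keep the calendar figure and label it treatment duration.
- Add days on drug, defined as that duration minus the days between interruption start and resumption, by dose group.
- Summarize it with n, mean, SD, median, minimum and maximum, and not only in the existing week categories.
- State that isolated missed doses remain in the compliance measure.

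In SAP 19.1, add to the overall TEAE summary, by dose group, the number and percentage of subjects with a TEAE whose recorded action was study drug interrupted or dose changed.

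First check the shells for an existing row. Separately, check protocol Amendment 4 for the dose-by-duration sentence, and name the output that answers it if the sentence is still there.

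The cost is SAP wording and a few table rows, with no new data and no change to trial conduct. Reported exposure may look slightly less favourable.

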18.1. DERIVATIONS

The extent of exposure in days will be calculated as:

$$\text{Extent of exposure (days)} = (\text{date of last study drug administration} - \text{date of first study drug administration}) + 1.$$

The date of first study drug administration is collected on the eCRF “First SC Injection” form. The date of last study drug is collected on the eCRF “End of Treatment” form.

19. SAFETY OUTCOMES

All outputs for safety outcomes will be based on the Safety Analysis Set.

There will be no statistical comparisons between the treatment groups for safety data.

19.1. ADVERSE EVENTS

Adverse Events (AEs) will be coded using *Medical Dictionary for Regulatory Activities (MedDRA) central coding dictionary, Version 19.1*. Investigator verbatim as well as preferred terms and system organ classes will be included in the listings.

Treatment-emergent adverse events (TEAEs) are defined as AEs that started or worsened on or after the date of first dose for treatment arms and adverse events that started or worsened on or after the baseline visit for standard of care group. For events that start or worsen on the date of

Document:	\\quintiles.net\Enterprise\Apps\sasdata\SASa\sas\Shire\Teduglutide\Biostatistics\Documentation\SAP\TE D-C14-006_SAP_Final_V1.0_20170714		
Author:	PPD	Version Number:	Final V1.0
		Version Date:	14Jul2017
Template No:	CS_TP_BS016 – Revision 3	Reference:	CS_WI_BS005
Effective Date:	01May2012		

first dose, any available start time will be compared to the time of first dose for the treatment arms.

See [Appendix 2](#) for handling of partial dates for AEs. In the case where it is not possible to define an AE as treatment-emergent or not, the AE will be classified by the worst case; i.e. treatment-emergent.

An overall summary of number of subjects within each of the categories described below will be provided as specified in the templates. Adverse events will be summarized using descriptive statistics (e.g., number and percentage of subjects) for each treatment arm and dose group. The number of events will also be presented except for summaries by highest category. The summary will include any TEAE, severity of TEAEs (highest category), investigator assessment of relationship of TEAEs to study drug, treatment-emergent serious AEs (TESAEs), investigator assessment of relationship of TESAEs to study drug, TEAEs leading to discontinuation and TEAEs leading to death.

Listings will include both TEAEs and Non-TEAEs (unless specified otherwise) and will be provided for serious adverse events, adverse events leading to death, and adverse events leading to discontinuation of study drug. Listings will indicate whether an AE is treatment emergent or not.

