3 STUDY DESIGN

3.1 Overall Design and Control Methods

This will be a double-blind, 2-arm study in which subjects will be randomized in a 1:1 ratio to receive either 0.025 mg/kg/day or 0.05 mg/kg/day of teduglutide for 24 weeks followed by 4 weeks of no active therapy. Dosing regimens will be blinded to both investigators and subjects. In addition, an attempt will be made to enroll subjects in a separate standard of care group, which will serve as an observational cohort for the 24-week treatment period and 4-week follow-up. The subjects in the standard of care group will follow the same visit schedule as the randomized subjects.

All subjects will be screened for a minimum of 2 weeks prior to start of treatment to verify the requirements for nutritional support for each subject and to ensure adherence to eligibility parameters. After screening, the 24-week treatment period will consist of visits at baseline, weekly for the first 2 weeks (Weeks 1 and 2), and then every other week through Week 12 (Weeks 4, 6, 8, 10, and 12). For the remainder of the treatment period, visits at the sites will be conducted every 3 weeks (at Weeks 15, 18, 21, and 24). Telephone contacts will be made on all other weeks during the treatment period. At all site visits and telephone contacts, safety will be monitored and nutritional support will be reviewed and adjusted as needed. A final visit will be scheduled at Week 28, 4 weeks following the end of treatment (EOT). Telephone contact will be made during the interim weeks from EOT to end of study (EOS), to monitor safety and any changes in nutritional support. If necessary, unscheduled visits can be arranged in place of the telephone contacts. Schedules of study parameters are displayed in [Table 6-1](#) and [Table 6-2](#).

To maintain consistency across all centers, sites and subjects (treated and standard of care) must follow the nutritional support adjustment guidelines (developed with SBS expert input and provided in [Appendix 1](#)) for decisions regarding PN/IV support reduction and advances in enteral feeds based on weight gain, urine, and stool output in the setting of clinical stability.

[figure not shown]
At the conclusion of the follow-up period (Week 28), if subjects are determined to have positive/specific antibodies, they will be asked to return for a follow-up visit 3 months post EOT for another antibody sample. If the subjects continue to have positive/specific antibodies

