support will be reviewed and adjusted as needed. At the end of the treatment period (week 24/EOT), all subjects will enter a 4-week follow-up period until the end of study (week 28/EOS) during which time no study drug (ie, teduglutide) will be administered. A final visit will be scheduled at week 28, 4 weeks following week 24 or the end of treatment (EOT). Telephone contact will be made during the interim weeks from EOT to end of study (EOS) to monitor safety and any changes in nutritional support.

To maintain consistency across all centers, sites and subjects (randomized and standard of care) should be made to follow the nutritional support adjustment guidelines (developed with SBS expert input and provided in the protocol) for decisions regarding parenteral nutrition/intravenous fluid (PN/IV) support reduction and advances in enteral feeds based on weight gain, urine and stool output, and clinical stability.

Document:	\\quintiles.net\Enterprise\Apps\sasdata\SASa\sas\Shire\Teduglutide\Biostatistics\Documentation\SAP\TE D-C14-006_SAP_Final_V1.0_20170714		
Author:	PPD	Version Number:	Final V1.0
		Version Date:	14Jul2017

[figure not shown]
Template No: CS_TP_BS016 – Revision 3
Effective Date: 01May2012

Reference: CS_WI_BS005

Copyright © 2012 Quintiles Transnational Corp. All rights reserved.

The contents of this document are confidential and proprietary to Quintiles Transnational Corp. Unauthorized use, disclosure or reproduction is strictly prohibited.

Table A Study Diagram

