19.1.2. SERIOUS ADVERSE EVENTS

Serious adverse events (SAEs) are those events recorded as “Serious” on the Adverse Events Form of the eCRF. Any SAE that occurs from the time of the signing of the ICF through last study visit (week 28 or EOS) will be captured. A summary of TESAEs by SOC and PT will be prepared, as well as summaries by event and causal relationship to study drugs. A listing of SAEs will be presented.

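### The treatment-emergent AE tables pool on-drug events with events arising in the planned 4-week no-drug period, and no AE summary described in the SAP separates them

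*SAP*

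**What the plan says.** - **Start of the window.** SAP 19.1: "Treatment-emergent adverse events (TEAEs) are defined as AEs that started or worsened on or after the date of first dose" for the dose arms, and "adverse events that started or worsened on or after the baseline visit for standard of care group". No end is given. Where the status of an event cannot be settled, "the AE will be classified by the worst case; i.e. treatment-emergent".
- **Off-drug period.** Protocol 3.1 plans dosing "for 24 weeks followed by 4 weeks of no active therapy". SAP 4.1 describes the follow-up from Week 24 to Week 28 as a period "during which time no study drug (ie, teduglutide) will be administered".
- **AE recording.** Protocol 6.1.1.2 records AEs "through the last study visit (Visit 28 or EOS". In Protocol Table 6-2, Visit 28 is a telephone contact and the Week 28 visit is Visit 30. I read the text as Week 28, in line with SAP 19.1.2: "Any SAE that occurs from the time of the signing of the ICF through last study visit (week 28 or EOS) will be captured".
- **AE summaries.** SAP 19.1 to 19.1.4 describe summaries by treatment arm and dose group, by system organ class (SOC) and preferred term (PT), and by severity, relationship and seriousness. None is by period.
- **End date already defined.** SAP Appendix 2 sets a reference end date: the last dose, or for standard of care the last visit within the 24-week period. It serves the imputation of medication dates and is not used in the treatment-emergent rule. SAP 18.1 ends exposure at the last dose.

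**The concern.** The tables merge two safety questions: what happens while a child receives the drug, and what happens after it is withdrawn, possibly with parenteral support already reduced. Protocol 6.1.1.1 counts worsening of the disease as an AE. Protocol Appendix 1 lists loss of weight or growth velocity, diarrhea and electrolyte imbalance as signs of deterioration. Such an event after the last dose enters the dose group's treatment-emergent counts beside on-drug events.

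The SAP treats the off-drug weeks as informative elsewhere. Section 17.2.1.6 plans changes from end of treatment (EOT) to EOS in parenteral and enteral support and in citrulline. AEs have no counterpart. Exposure stops at the last dose while the AE count runs to EOS, so the exposure and AE tables cover different periods. Counting standard of care over the same nominal 28 weeks does not separate the two questions, because that group has no drug to withdraw.

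**Working it through.** The documents give no figure that depends on this rule, so there is none to reproduce. The check sets the dates side by side and then sizes the effect.

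**1. Share of the window that is off drug.** Inputs: EOT at Day 168 and EOS at Day 196 (Protocol Table 6-2); a child who stops early returns 4 weeks later (Protocol 4.4).

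- Completer: (196 − 168)/196 = 28/196 = 14.3%.
- Child stopping at Week w: 4/(w + 4). Week 4: 4/8 = 50%. Week 8: 4/12 = 33.3%. Week 12: 4/16 = 25%. Week 18: 4/22 = 18.2%.

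These are shares of time, not of events.

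**2. Extra count if the event rate does not change after stopping.** Assumptions: constant hazard, all children complete, 24-week incidence p taken across a range because the documents give none. Arm size 10 is the minimum in Protocol 4.1. Formula: incidence to Week 28 = 1 − (1 − p)^(28/24).

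| p at 24 weeks | Counted to Week 28 | Extra points | Extra children per 10 |
|---|---|---|---|
| 10% | 11.6% | 1.6 | 0.16 |
| 20% | 22.9% | 2.9 | 0.29 |
| 30% | 34.0% | 4.0 | 0.40 |
| 50% | 55.5% | 5.5 | 0.55 |
| 70% | 75.5% | 5.5 | 0.55 |
| 90% | 93.2% | 3.2 | 0.32 |

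With s = 1 − p, the excess s − s^(7/6) peaks at s = (6/7)^6 = 0.397, where it is 0.397/7 = 5.7 points. The range is therefore about 0.2 to 0.6 children per arm of 10.

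**3. If events rise after stopping.** Constant hazard assumes no withdrawal effect, so a hypothetical contrast helps. Take 20% on drug over 24 weeks and an independent 4-week off-drug incidence x. The pooled table shows 1 − 0.8(1 − x): 28% for x = 10%, 36% for x = 20%, 44% for x = 30%. Constant hazard would give x = 1 − 0.8^(4/24) = 3.7%. The table shows only the pooled figure, so 36% could equally be an on-drug incidence of 36%.

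**4. Merging within a child.** Suppose a child has a mild event at Week 6 and a severe one of the same term at Week 26. The subject incidence counts one child. Under SAP 19.1.1.1 the severity summary shows only severe, with nothing to say that it arose off drug. SAP 19.1 also presents event counts except in highest-category summaries, so the recurrence adds an event there, still without a period.

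**The case against.** **Withdrawal is examined elsewhere.** A reader might infer that effects of stopping the drug cannot be seen at all. The documents do not support that. Parenteral and enteral support are summarized through follow-up (SAP 17.2.1.3 and 17.2.1.5), and EOT-to-EOS changes are planned for both and for citrulline (17.2.1.6). Laboratory values and weight are tabulated by site visit (19.2 and 19.6), and Week 28 is a site visit that collects them. Onset day and last-dose date are available (7.1 and 18.1). This stands, and it confines the gap to the AE summary tables.

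**A window of about 4 weeks after the last dose is defensible.** Protocol 6.1.2 captures serious AEs to 4 weeks after the last dose, and over-inclusion is the cautious direction. In practice AE recording stops at EOS, so the open-ended rule has an effective end. This also stands. The missing end is a wording gap, and pooling is a legitimate overall display if a split accompanies it.

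**The half-life does not settle where to cut.** A reader might infer from the half-life of about 2 hours in Protocol 1.1 that events from the day after the last dose cannot be drug effects. That figure is plasma elimination. The same section describes a structural effect on the intestinal lining, and the documents do not say how long it lasts.

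**Not everything can be checked.** Table shells are in a separate file, and the SAP cites Protocol Amendment 4 while the supplied protocol's history ends at Amendment 2. A split or a bound could exist there; the SAP text contains neither.

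**Conclusion.** The point holds as a reporting gap in the AE summary tables. AEs from the no-drug period are pooled with on-drug AEs, that period is 14.3% of a completer's window and more for an early stopper, and no AE summary in the SAP text separates the two.

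The average effect on counts is modest: about 0.2 to 0.6 children per arm of 10, under constant hazard and full completion. The plan gives no early-stopping rate, so the larger shares for early stoppers are illustrations. The better reason to act is that a cluster of post-withdrawal AEs, if there were one, would not show as such in any described AE table.

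A reader might infer that on-drug incidence is misreported. The tables report treatment-emergent AEs, not on-drug incidence, so nothing in them is wrong as labelled. No hypothesis testing is planned (SAP 8.4), so no error rate or power is affected. This is a low-cost improvement to the main safety display of a descriptive study.

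**What to change.** - Keep the overall treatment-emergent tables, and state in SAP 19.1 that the window ends at EOS.
- Add a split by onset period to the overall, SOC/PT and serious AE tables: first dose through the Appendix 2 reference end date, and after it to EOS. Split standard of care at its own reference end date, starting from the baseline visit.
- Count a term in each period in which it starts or worsens, so that an off-drug recurrence or worsening is not absorbed. This needs a dated record of worsening, as the present rule already does.
- State how a partial onset date is assigned to a period. The AE date rules in Appendix 2 were written around the reference start date only.
- Label the second period post-treatment, without claiming that drug effect is absent, and do not justify the cut by the half-life.

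The dates needed are already collected, so the cost is SAP wording and one flag. The downside is longer AE tables, with small counts in the post-treatment columns that should be read case by case.
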